7.3 Lost to Follow-Up

1. We will provide clear communication about the importance of follow-up visits with some incentives for participation and maintaining regular contact with participants through phone calls, emails or reminders.
2. Offer flexibility in scheduling
3. Follow up duration will be 4 weeks after a lack of response. We will re-attempt to contact the survivor after a brief 2 week pause after which we will no longer contact the survivor.

Section 8: TRIAL ASSESSMENTS AND PROCEDURES

This section outlines the comprehensive assessments and procedures deployed throughout the trial to ensure accurate, reliable data collection across all specified endpoints, emphasizing adherence to the trial's design and objectives.

Data Collection and Assessment Methods

- Claims Record: To accurately assess the financial impact of the intervention on healthcare expenditures, participants will be requested to provide Claims Records and Explanation of Benefits documentation. This comprehensive data set will

encompass costs related to hospitalization, medication, lab visits, and other relevant medical expenses.

- **Electronic Health Records (EHR):** For a detailed and objective view of medical histories, participants will be asked to access their Electronic Health Records through platforms like MyChart. This step aims to enrich the claims data with additional medical record insights with information like days of hospitalization, disease for which treatment was undertaken, whether it was an Emergency visit or not and so on.
- **Patient-Reported Outcomes:** In a complementary approach to objective data collection, participants will also self-report on various aspects including healthcare expenditures, treatment adherence (using the MMAS-8 scale), quality of life (measured by FACT-G), pain levels (assessed through the Brief Pain Inventory), sleep quality (evaluated by PROMIS), physical activity capabilities (determined by GLTEQ), and cancer progression status. Furthermore, they will report on absenteeism (detailing the number of leave days taken, including short-term or long-term disability status) and presenteeism (evaluated through work motivation and performance review scores). These self-reported metrics will be securely collected through a digital platform, aiming to supplement and validate the analysis of claims and EHR data.

Live Coaching Consistency

- **Training Program for Live Coaches:** To ensure uniform delivery of the intervention across participants, live coaches will undergo a standardized training program. This program will cover the intervention's core components, ethical guidelines, communication skills, and use of the digital platform for interaction with participants. Regular refresher sessions and assessments will maintain coaching quality and consistency.

Ensuring Data Integrity and Consistency

- Centralized Data Collection: Utilizing a centralized digital platform for self-reported data and integrating EHR information will ensure data consistency and facilitate real-time monitoring of trial progress.
- Standardized Assessments: All assessments, including all the self-reported metrics, will be conducted following standardized protocols. Instructions on the timing and conditions of assessments will be clearly communicated to participants, and specialized training will be provided to any personnel involved in data collection or analysis.
- Blinding Maintenance: While blinding participants to the intervention details is not feasible, measures will be in place to ensure that data analysts and the Trial Monitoring Committee members are blinded to group assignments to minimize bias in outcome assessment and safety monitoring.

8.1 Screening/Baseline Assessments and Procedures

1. Informed Consent Process:
 - We will obtain informed consent from participants, ensuring they understand the nature of the trial, potential risks and benefits, and their rights as participants.
2. Medical History and Physical Examination:
 - We will collect relevant medical history information, including past medical conditions, current medications, surgical history from the survivor.
3. Work-related Assessments:
 - We will conduct baseline assessment on pre-cancer work data - work hours, number of sick days taken; current status - if and since when they are on short term or long term disability from the survivor
4. Disease Assessment and Staging:
 - We will collect survivor reported disease assessments specific to the cancer types under study, such as tumor staging, biomarker evaluations, or imaging studies to assess baseline disease status and severity.
5. Stratification Variables:

- See section 5.3 for Trial population variables and section 4.1 for Randomization variables.

8.2 Efficacy Assessments and Procedures

Healthcare Expenditure Reduction (Trial Objective 1):

- Endpoint: Total healthcare expenditure, including hospitalization costs, medication expenses, outpatient visits, etc.
- Assessment Procedure: Conduct comprehensive assessments of healthcare expenditure for participants in both the intervention and control groups at specified time points (e.g., baseline, 3 months, 6 months, 12 months and 18 months).
- Data Collection: Obtain detailed data on healthcare utilization, costs of medical services, medication expenses, and related healthcare expenditures through EHR access granted by participants, and participant-reported information.
- Analysis: Calculate the mean total healthcare expenditure for each group and compare the differences between the intervention and control groups over the trial period.

Impact on Adherence to Treatment (Trial Objective 2):

- Endpoints: Change in MMAS-8 scores
- Assessment Procedures: Administer the MMAS-8 questionnaire to assess adherence levels to treatment regimen at baseline and specified time points during and after the intervention period.
- Data Collection: Obtain self-reported scores from participants on adherence levels.
- Analysis: Calculate the mean difference in change in survey scores between the intervention and control groups at each time point to evaluate the impact

Improvement in Quality of Life Score (QoLS), Pain, Sleep and physical activity (Trial Objective 3):

- Endpoint: Change in FACT-G, GLTEQ, BPI-ShortForm, PROMIS scores measuring quality of life, physical activity, pain levels, and sleep
- Assessment Procedures: Administer the above four questionnaires to assess participants' at baseline and specified time points during and after the intervention period.
- Data Collection: Obtain self-reported scores from participants on Quality of Life, Pain levels, and behavior change specifically with Healthy Diet intake and ability to do physical activity.
- Analysis: Calculate the mean difference in change in scores between the intervention and control groups at each time point to evaluate the impact of the intervention.

Reduction in Employee Absenteeism (Trial Objective 4):

- Endpoint: Number of leave days taken by employed cancer survivors due to health issues.
- Assessment Procedures: Track the number of leave days (sick leave, short-term disability, long-term disability) taken by participants in both groups throughout the trial period.
- Data Collection: Obtain leave records from participants' employers or self-reported information from participants.
- Analysis: Compare the average number of leave days between the intervention and control groups to assess the impact of the intervention on reducing absenteeism.

Improvement in Employee Presenteeism (Trial Objective 5):

- Endpoints: Motivation to work (self-reported scales/questionnaires), performance review scores (from employer records or self-reported evaluations).
- Assessment Procedures: Administer self-reported scales/questionnaires to assess participants' motivation to work and obtain performance review scores from employer records or self-reported evaluations.

- Data Collection: Collect self-reported data on motivation to work and obtain performance review scores from participants and their employers.
- Analysis: Compare the mean scores of motivation and performance reviews between the intervention and control groups to evaluate the impact of the intervention on enhancing presenteeism.

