6.1 Schedule of Events

Schedule of events for test/treatment group:

		Week	Week	Month 1-6	Month 7-18
Intervention or Assessment (Test)	Baseline (Day -30 to -1)	1/3/5/7/9/11/13/15/17/19/21/23	2/4/6/8/10/12/14/16/18/20/22/24	(Every 30 days)	(Every 30 days)

Live 1:1 Lifestyle Coaching - 3-5 days per week, 45 mins each		X	X		
Async access to Lifestyle modification content curated by CT		X	X		
Informed Consent	X				
Eligibility Criteria Assessment	X				
Demographic Details	X				
EHR Access Consent	X				
Claims Data Access	X		X		X
QoLS (FACT-G Form)	X		X		X
Weight	X		X		X
Physical Activity (GLTEQ)	X		X		X
Pain (BPI-ShortForm)	X	X	X		X
PROMIS (Short Form)	X	X			X
Adherence	X	X			X

(MMAS-8)					
Motivation to work	X	X			X
Employee Performance Review	X	X			X
Absenteeism Questions	X	X			X
Claim data validation with survivor				X	X
Cancer Progression Status				X	X

Schedule of events for active comparator (control) group:

Intervention or Assessment (Test)	Baseline (Day -30 to -1)	Week 1/3/5/7/9/11/13/15/17/19/21/23	Week 2/4/6/8/10/12/14/16/18/20/22/24	Month 1-6 (Every 30 days)	Month 7-18 (Every 30 days)
Async access to publically available lifestyle modification guidance		X	X		
Informed Consent	X				
Eligibility Criteria Assessment	X				
Demographic Details	X				
EHR Access Consent	X		X		X
Claims Data Access	X		X		X
QoLS (FACT-G Form)	X		X		X
Weight	X		X		X
Physical Activity	X		X		X

(GLTEQ)					
Pain (BPI-ShortForm)	X	X	X		X
PROMIS (Short Form)	X	X			X
Adherence (MMAS-8)	X	X			X
Motivation to work	X	X			X
Employee Performance Review	X	X			X
Absenteeism Questions	X	X			X
Claim data validation with survivor				X	X
Cancer Progression Status				X	X

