 - Analysis will consider any change in employment status as an intercurrent event, with a modified intention-to-treat analysis excluding participants who lose their job unrelated to health status.
 - Handling of Missing Data:
 - Worst-case scenario imputation for missing absenteeism data, assuming maximum observed absence for missing periods.
 - Sensitivity Analysis:
 - Repeating analyses with and without worst-case imputation to evaluate the impact of different missing data assumptions on the outcome.
- **Secondary Objective 4: Impact on Employee Presenteeism**
 - Statistical Model and Hypothesis:
 - Model: Mixed-effects models to analyze changes in work motivation and performance review scores over time.
 - Hypothesis: H0: No difference in changes in motivation and performance scores between groups. H1: Significant improvement in these measures in the intervention group.
 - Handling of Intercurrent Events:
 - Job changes or significant alterations in work responsibilities will be documented and explored in sensitivity analyses to understand their impact on presenteeism outcomes.
 - Handling of Missing Data:
 - LOCF for interim missing data points in motivation and performance scores, acknowledging potential limitations in this approach.
 - Sensitivity Analysis:

- Analysis excluding participants with significant job changes during the trial to assess the effect of such changes on presenteeism outcomes.

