9.7 Sample Size Determination

- The metric-wise sample size calculation is provided in the table below on alpha as 0.05 and power of 80% for the one-tail test at enrollment ratio = 1.

- While we are conducting the power analysis and sample size calculation based on several variables (outcomes) of interest, the sample size was computed separately for each parameter in the study and the greatest is used to obtain sample size.
- The analysis (detailed below in table) showed that sample of size of 102 is powerful enough for the analysis to cover 100% of primary and secondary metrics.
- Now since we believe that the long follow-up duration of 12 months for our trial will lead to around 30% drop-offs, we decided a final sample size of 146 (73 control, 73 test).
- So even if get 30% or 44 participants drop off we end up with final sample set of 102 (51 control, 51 test) and would be able to come to statistically significant effects ($p < 0.05$) with respect to 100% of primary and secondary metrics.

Metric Segment	Sub Metric	Control Data	Test Data	Assumed Variance	Sample Size
Primary Outcome / Concerns					
Medical Expenditure	Total Healthcare Expenditure (Planned + Unplanned)	10000	8000	Variance of 4000	102 (51 Control, 51 Test)
	No of Urgent Care Visits	3	2.5	Variance of 0.5	28 (14 Control, 14 Test)
	No of ED Visits	5	3.45	Variance of 0.8	10 (5 Control, 5 Test)
	No of unplanned outpatient/office	4.28	3.5	Variance of 0.8	28 (14 Control, 14 Test)

	visits (other than ED)				
	Unplanned Hospitalisations	5	4	Variance of 0.8	18 (9 Control, 9 Test)
	Length of hospital stay	3	2	Variance of 0.8	18 (9 Control, 9 Test)
	No of planned outpatient visits	2	1.8	Variance of 0.3	58 (29 Control, 29 Test)
	No of planned hospital visits	1.25	1	Variance of 0.1	10 (5 Control, 5 Test)
	Length of hospital stay	3	2	Variance of 0.8	18 (9 Control, 9 Test)
	Total Prescription Medicine Expenditure	1000	950	Variance of 80	80 (40 Control, 40 Test)
Secondary Outcome / Concerns					
Adherence	MMAS scale	4.5	7	Variance of 2.5	28 (14 Control, 14 Test)
QoLS Score, Pain Levels, Sleep Quality, Physical Activity	QoLS Score (FACT-G)	70	85	Variance of 20	42 (21 Control, 21 Test)
	Brief Pain Inventory (Short Form)	80	60	Variance of 35	78 (39 Control, 39 Test)

	PROMIS (Short Form)	70	55	20	46 (23 Control, 23 Test)
	GLTEQ	25	17	10	42 (21 Control, 21 Test)
	Calorie Burnt	120	198	Variance of 70	22 (11 Control, 11 Test)
Presenteeism	Attitude towards work	2	4	Variance of 1.5	16 (8 Control, 8 Test)

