	Employee Performance	0.6	0.7	Variance of 20%	102 (51 Control, 51 Test)
Cancer Care	Cancer Progression Status	0.85	0.88	Variance of 0.04	46 (23 Control, 23 Test)
	Cancer recurrence status	0.3	0.21	Variance of 10%	32 (16 Control, 16 Test)
Absenteeism	Working Hours	30	40	Variance of 10	28 (14 Control, 14 Test)
	Vacation Days	0.5	0.3	Variance of 0.15	16 (8 Control, 8 Test)

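### Performance review scores are collected without issue date or covered period, so employer reviews of pre-randomization work can count as on-trial outcomes and bias the arm difference toward zero

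*Combined protocol and SAP*

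**What the plan says.** In the Combined protocol and SAP, the schedule in section 6.1 lists "Employee Performance Review" at baseline, at the odd weeks 1 to 23, and every 30 days in months 7 to 18, in both arms. That is 12 + 12 = 24 post-baseline entries. Section 8.2 allows two sources: staff are to "obtain performance review scores from employer records or self-reported evaluations". Section 3 allows the same two and defines the estimand as the difference in mean scores over the trial period.

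Section 9.3 plans "Mixed-effects models to analyze changes in work motivation and performance review scores over time" and fills interim missing motivation and performance scores by LOCF.

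Section 9.7 sizes each metric at "alpha as 0.05 and power of 80% for the one-tail test at enrollment ratio = 1", and "the greatest is used to obtain sample size". The row "Employee Performance" has 0.6 against 0.7, a spread given as "Variance of 20" per cent, and 102 participants (51 per arm).

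The separate Protocol has the same two sources and the same LOCF rule. Its odd-week column runs on to week 47.

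Neither document asks when a review was issued or what period it covers, says which source takes precedence, or says what to enter when no new review has appeared since the last visit.

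**The concern.** Employers review staff on their own cycle, not every two weeks. When the employer record is the source, the latest available review at an early visit may have been written before randomization, or may mostly cover work done before it. If staff leave the visit blank until a new review appears, the LOCF rule puts the baseline score there. By either route, a score that the programme could not have influenced is analysed as an on-trial value.

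The expected bias is toward no difference. Because no dates are collected, affected scores cannot be identified or removed later. Early data are the most exposed, and section 9.6 plans interim looks at primary and secondary efficacy at 3, 6 and 12 months. Section 9.7 also claims significance for every primary and secondary metric with 102 completers, which for this row presumes scores that reflect on-trial work.

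**Working it through.** **1. Reproduce the planned size.** Inputs from section 9.7: difference 0.7 − 0.6 = 0.10, one-sided alpha 0.05, power 80%, 1:1 allocation. The stated size is matched only if the 20% is used as a standard deviation of 0.20, so the standardized effect is 0.10 / 0.20 = 0.5.

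- Normal approximation: n = 2 × (1.645 + 0.842)² × (0.20 / 0.10)² ≈ 49.5, or 50 per arm.
- Two-sample t-test: 50.15, rounded up to 51 per arm, 102 in total. This matches the plan.
- Dropout of 30%: 102 / 0.70 = 145.7, or 146. This also matches.
- Power at 51 per arm is 80.6%, so there is almost no slack.

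**2. Dilution by an assumed share.** Let *f* be the share of analysed scores that describe pre-randomization work. The documents do not give *f*; it is an assumption, taken as equal in both arms, with the standard deviation held at 0.20. The expected difference becomes 0.10 × (1 − *f*).

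| *f* | Difference | Power at 51 per arm | Total for 80% power | After 30% dropout |
|---|---|---|---|---|
| 0 | 0.10 | 80.6% | 102 | 146 |
| 10% | 0.09 | 73% | 124 | 178 |
| 20% | 0.08 | 64% | 156 | 223 |
| 30% | 0.07 | 54% | 204 | 292 |
| 50% | 0.05 | 35% | 398 | 569 |

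**3. How far the result depends on the review cycle.** Assume that every score is an employer review, that review dates are spread evenly over a cycle of L months, and that the effect is proportional to the on-trial part of the reviewed period. For t up to L months, the mean on-trial share is t² / (2L²).

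- L = 12: month 3, 9/288 = 3%; month 6, 36/288 = 12.5%; month 12, 144/288 = 50%. At month 18, half the reviews lie wholly on trial and the other half average 75%: 0.5 × 1 + 0.5 × 0.75 = 87.5%. Single-visit power is 6%, 9%, 35% and 71%.
- L = 6: month 3, 9/72 = 12.5% (power 9%); month 6, 36/72 = 50% (35%); from month 12, 100% (80.6%).
- L = 1: no loss from month 3.

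These are t-tests at one visit with 100% employer records. They show how sensitive the endpoint is; they are not the power of the planned mixed model.

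**4. What else needs 102.** In the Combined protocol and SAP, Total Healthcare Expenditure (10000 against 8000, spread 4000) has the standardized effect 2000 / 4000 = 0.5 and also needs 102. In the Protocol, expenditure is exploratory, and Employee Performance is the only primary or secondary metric at 102.

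**The case against.** The strongest reply is that the documents never instruct anyone to enter an old review. They allow self-report, and several places point to it as a main route: section 8 lists presenteeism among participant-reported outcomes, section 6.7 puts all outcome metrics under patient-reported outcomes, and section 11.2 describes an in-app form. Self-reports could be current. This stands, and it limits the point to scores taken from employer records and to the baseline score carried forward. It does not remove the gap, because nothing requires a self-report to refer to recent work or says which source takes precedence.

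Second, the steep early losses in step 3 are not losses against a stated claim. Section 9.7 does not tie its 80% to month 3 or month 6, the estimand covers the trial period, and the analysis is a mixed model. The plan also does not say that the 0.10 difference excludes dilution. All of this stands, which is why the size is given only as a range.

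Third, entering the same review repeatedly does not by itself create false precision if the model handles within-person correlation. This also stands; the issue is attenuation, not a raised type I error.

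A reader might also infer that this endpoint alone sets the trial's size. In the Combined protocol and SAP it does not: expenditure ties at 102, so repairing or dropping this row leaves 102 and 146 unchanged.

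**Conclusion.** The point holds as a gap in data collection and missing-data handling for a secondary endpoint. The plan does not exclude employer scores for pre-randomization work from the post-baseline data, its LOCF rule can carry the baseline score into post-baseline visits, and without dates the problem cannot be put right at analysis.

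The expected direction is toward no difference. The size rests on two unknowns, the review cycle and the employer/self-report mix. Under the assumptions of step 2, 10% to 20% pre-randomization scores reduce power at 51 per arm from 80.6% to about 73% to 64%. With short review cycles or mostly current self-reports the loss could be negligible.

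The documents do not support saying that pre-randomization reviews are entered by rule, or that power at the early looks is known to be 6% or 9%. In the Protocol this row does stand alone among primary and secondary metrics at 102, so the power statement for it matters more there.

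**What to change.** - **Section 8.2:** record the source, issue date and period covered for each performance score. Treat any review issued before randomization as baseline only. Enter each employer review once, at its issue date.
- **Section 9.3:** do not use LOCF to carry a baseline or repeated employer review into post-baseline visits; leave those visits missing in the mixed model. Analyse reviews whose period straddles randomization together with the others, and add a sensitivity analysis limited to reviews whose period lies wholly after randomization.
- **Section 9.7:** state that the 80% power for this row assumes scores that reflect on-trial work.

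Make the same changes in both documents.

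Two stronger remedies are not advised. Requiring the whole period to follow randomization in the main analysis would, under an annual cycle with even timing, leave about half the sample at month 18. That is 25 or 26 per arm and single-visit power of about 54% to 55%, against 71% with straddling reviews kept. Replacing the endpoint with a two-week self-rating would expose it to reporting bias, since section 8 concedes that participants cannot be blinded to the intervention details, and no mean or standard deviation is given for such a measure.

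The cost is two or three extra form fields, a few sentences, and fewer early post-baseline employer scores. Leaving visits missing also relies on the mixed model's missing-at-random assumption, which should be stated.

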8.3 Safety Assessments and Procedures

- Responsibilities
 - The Trial Monitoring Committee will oversee safety assessments and procedures throughout the trial.
- Safety Data Collection
 - Safety data will be collected through self-reported participant interviews.
 - Standardized forms and procedures will be used for consistent data collection across study sites.
- Safety Reporting and Management
 - Procedures will be in place for the timely reporting and management of safety events, including serious adverse events (SAEs) and suspected unexpected serious adverse reactions (SUSARs).
- Safety Monitoring Committee
 - The Trial Monitoring Committee will review safety data periodically, assess participant safety, and provide recommendations to the study team.
- Participant Education and Counseling
 - Participants will receive education and counseling regarding potential safety risks associated with the intervention.
 - Open communication between participants and study staff will be encouraged to facilitate early detection and reporting of safety events.
- Risk Mitigation Strategies
 - Risk mitigation strategies will be implemented to minimize potential safety risks associated with the intervention, such as user training and device monitoring.

- Adherence to safety protocols will be monitored, and interventions will be implemented to address deviations or non-compliance.
- Regulatory Compliance
 - Compliance with regulatory requirements governing safety reporting will be ensured, including adherence to Good Clinical Practice (GCP) guidelines and ICH regulations.
 - Accurate and comprehensive safety documentation will be maintained, including safety reports and investigator brochures.

